**Table 1: Power to detect a treatment difference in HiSCR50 at Week 16 in Part 1**

Placebo	Treatment Group	Difference	Power
Bermekimab 1050 mg (n=50)/Adalimumab (n=50) vs placebo (n=50)			
25%	50%	25%	83%
25%	55%	30%	93%
25%	60%	35%	97%
25%	65%	40%	99%
25%	70%	45%	>99%
25%	75%	50%	>99%
30%	55%	25%	81%
30%	60%	30%	92%
30%	65%	35%	97%
30%	70%	40%	99%
30%	75%	45%	>99%
35%	60%	25%	81%
35%	65%	30%	92%
35%	70%	35%	97%
35%	75%	40%	99%

**Table 2: Confidence interval for the treatment difference in HiSCR at Week 16 in Part 1**

HiSCR (P1)	HiSCR (P2)	Difference (P1 – P2)	Width	Confidence Limit	Confidence Level
Bermekimab 1050 mg qw dose regimen (n=50; P1) vs adalimumab (n=50; P2)					
60%	50%	10%	29.3%	(-4.7%,24.6%)	80%
65%	50%	15%	29.0%	(0.5%,29.5%)	80%
70%	50%	20%	28.6%	(5.7%,34.3%)	80%
75%	50%	25%	27.9%	(11.0%, 38.9%)	80%

**Table 3: Power to detect a treatment difference in HiSCR50 at Week 12 Combining Part 1 and Part 2**

Placebo	Treatment Group	Difference	Power
Bermekimab 1050 mg (n=125) vs placebo (n=75)			
25%	50%	25%	97%
25%	55%	30%	>99%
25%	60%	35%	>99%
25%	65%	40%	>99%
25%	70%	45%	>99%
25%	75%	50%	>99%
30%	55%	25%	97%
30%	60%	30%	99%
30%	65%	35%	>99%
30%	70%	40%	>99%
30%	75%	45%	>99%
35%	60%	25%	96%
35%	65%	30%	99%
35%	70%	35%	>99%
35%	75%	40%	>99%
Bermekimab 700 mg (n=50) vs placebo (n=75)			
25%	50%	25%	89%
25%	55%	30%	96%
25%	60%	35%	99%
25%	65%	40%	>99%
25%	70%	45%	>99%
25%	75%	50%	>99%
30%	55%	25%	87%
30%	60%	30%	95%
30%	65%	35%	99%
30%	70%	40%	>99%
30%	75%	45%	>99%
35%	60%	25%	87%
35%	65%	30%	95%
35%	70%	35%	99%
35%	75%	40%	>99%

### 9.3. Populations for Analysis Sets

For the efficacy analyses in this study, the full analysis set (FAS) will be used according to the participants' assigned treatment to which they were randomized, regardless of the treatment they actually received. The FAS includes all randomized participants who receive at least one administration of study intervention. The FAS will be used for all primary and secondary efficacy analyses.

Safety analyses will include all participants who received at least 1 administration of study intervention and participants will be analyzed based on the treatment they actually received, regardless of the treatment groups to which they were assigned.

Pharmacokinetics analyses for bermekimab will include participants who receive at least one administration of bermekimab and have at least one post-dose sample collection. Antibodies to bermekimab will be analyzed for participants who receive at least one dose of bermekimab and have at least one post-dose sample collection.

## 9.4. Statistical Analyses

### 9.4.1. Statistical Methods

Simple descriptive summary statistics, such as n, mean, standard deviation (SD), median, interquartile range, minimum, and maximum for continuous variables, and counts and percentages for discrete variables will be used to summarize most data.

In general, treatment comparisons for binary endpoints will be performed using a Cochran-Mantel-Haenszel (CMH) test stratified by baseline Hurley stage status. For continuous efficacy endpoints, treatment comparisons will be performed using a Mixed-Effect Model Repeated Measure (MMRM) model. The MMRM will include treatment, visit, baseline value for the corresponding efficacy endpoint, baseline Hurley stage status, baseline value by visit interaction, baseline Hurley stage status by visit interaction and the treatment-by-visit interaction, if applicable. The Least Square mean (LSmean) estimates and their corresponding 95% CIs will be provided at each time point. In addition, the estimates of LSmean difference and 95% CIs between treatment groups will be provided.

In general, all statistical testing will be performed at a significance level of 0.05 (2-sided) unless otherwise specified. Nominal p-values will be displayed for all treatment comparisons.

### 9.4.2. Efficacy Analyses

#### 9.4.2.1. Primary Endpoint

The primary efficacy endpoint is the proportion of participants with a clinical response at Week 16 in Part 1, and at Week 12 in Part 2, defined according to the HiSCR50 measure as at least a 50% reduction from baseline in the total abscess and inflammatory- nodule count, with no increase in the abscess or draining fistula count.

##### 9.4.2.1.1. Primary Estimand 1

**Primary Estimand 1:** The primary estimand 1 (ie, a precise definition of the primary targeted treatment effect) is defined by the following 5 attributes:

- **Population:** adult participants with moderate to severe HS.
- **Variable/endpoint:** HiSCR50 binary responder variable at Week 16 in Part 1.
- **Treatment:**
  - Experimental: Bermekimab1050 mg qw.
  - Active Comparator: Adalimumab
  - Control: Placebo

- **Intercurrent Events and Corresponding Analysis Strategies:**

Intercurrent Events	Analysis Strategy for Addressing Intercurrent Events
1. Discontinuation of study intervention due to lack of efficacy or an AE of worsening of HS. 2. Initiation of a protocol-prohibited medication or therapy that could improve HS during the study.	Composite Strategy: Participants are considered HiSCR50 nonresponders at the time of primary endpoint if they experience this intercurrent event prior to Week 16 in Part 1.
3. Discontinuation of study intervention for other reasons.	Treatment policy strategy: Observed data will be used regardless of whether or not this intercurrent event had occurred.

Note: For participants experiencing multiple intercurrent events (ICEs), ICE 2 will override ICE 3.

- **Population level summary:** Difference in the proportions of participants achieving HiSCR50 at Week 16 in Part 1, between the bermekimab and placebo treatment groups.

#### 9.4.2.1.2. Primary Estimand 2

**Primary Estimand 2:** The primary estimand 2 is also defined by the following 5 attributes as the primary estimand 1:

- **Population:** adult participants with moderate to severe HS.
- **Variable/endpoint:** HiSCR50 binary responder variable at Week 12 based on the combined data from Part 1 and Part 2.
- **Treatment:**
  - Experimental: Bermekimab 700 mg qw→q2w (starting at Week 12), 1050 mg qw→q2w (starting at Week 12), and 1050 mg qw. For the primary analysis, bermekimab 1050 mg qw →q2w and 1050 mg qw groups will be combined as 1050 mg group and bermekimab 700 mg qw → q2w group will be denoted as 700 mg group.
  - Control: Placebo
- **Intercurrent Events and Corresponding Analysis Strategies:**

Intercurrent Events	Analysis Strategy for Addressing Intercurrent Events
1 Discontinuation of study intervention due to lack of efficacy or an AE of worsening of HS. 2 Initiation of a protocol-prohibited medication or	Composite Strategy: Participants are considered HiSCR50 nonresponders at the time of primary endpoint if they experience this intercurrent event prior to Week 12 in Part 1 and Part 2

therapy that could improve H S during the study.	
3 Discontinuation of study intervention for other reasons.	Treatment policy strategy: Observed data will be used regardless of whether or not this intercurrent event had occurred.

Note: For participants experiencing multiple ICEs, ICE 2 will override ICE 3.

- **Population level summary:** Difference in the proportions of participants achieving HiSCR50 at Week 12 based on the combined data from both Part 1 and Part 2 of the study between the bermekimab and placebo treatment groups.

#### 9.4.2.1.3. Primary Endpoint Analysis

In the primary efficacy analysis, data from all randomized participants who received at least 1 administration of study intervention will be analyzed according to their assigned treatment group.

In this primary analysis, the proportion of participants who achieve a HiSCR50 at Week 16 in Part 1, and at Week 12 based on the combined data from Part 1 and Part 2 will be summarized for each treatment group. To address the primary objective, a CMH chi-squared statistic stratified by baseline Hurley stage status (II, III) at an alpha level of 0.1 will be used for each of the comparisons between bermekimab treatment groups and placebo group.

There will be 3 comparisons for the primary analyses. The proportion of participants who achieve HiSCR50 will be compared between bermekimab treatment groups and the placebo group based on the fixed-sequence testing approach. To maintain an overall Type I error rate of 0.1, the 3-pairwise comparisons will be performed sequentially at a two-sided alpha level of 0.1 in the following order:

1. Bermekimab 1050 mg group versus Placebo at Week 12 based on the combined data from Part 1 and Part 2
2. Bermekimab 1050 mg group versus Placebo at Week 16 based on the data from Part 1
3. Bermekimab 700 mg group versus Placebo at Week 12 based on the combined data from Part 1 and Part 2

With the pre-specified sequential analyses, whenever a prior comparison is not significant at a two-sided alpha level of 0.1, the remaining treatment group comparisons will be considered nonsignificant and the p-values from the remaining treatment group comparison will be considered nominal.

In addition, the comparison between adalimumab and placebo for the primary endpoint at Week 16 in Part 1 will also be performed.

This method is to control the type-1 error at 10% level or less and will only be implemented for the primary efficacy analysis. The study will be considered positive if one of the hypotheses is tested as significant at a 2-sided alpha level of 0.10.

To examine the robustness of the primary endpoint analysis, additional analyses will be conducted using different missing data approaches; these analyses will be described in the SAP. In addition, sensitivity analyses will be performed for the primary endpoint using the per-protocol population, which includes participants who are generally compliant with the protocol.

To evaluate the consistency of the efficacy, subgroup analyses of the primary endpoint will be performed.

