### **6.3. Measures to Minimize Bias: Randomization and Blinding**

#### **Intervention Allocation**

##### ***Procedures for Randomization and Stratification***

Dynamic central randomization will be implemented in this study.

The randomization method will be a minimization procedure with biased-coin assignment for both randomizations, which minimizes the imbalance in the distribution of the number of participants across treatment groups within the levels of each individual stratification factor: investigational site and baseline Hurley stage status (II, III). Based on the algorithm, each participant will be assigned to the treatment group which will produce minimum total imbalance score with a high probability, where the total imbalance score is a weighted average of the imbalance scores for each stratification factor and for the whole study. The Interactive Web Response System (IWRS) will assign a unique treatment code, which will dictate the treatment assignment and matching study drug for the participant.

At first, approximately 150 participants in Part 1 will be randomized to receive bermekimab 1050 mg, adalimumab, or placebo in a 1:1:1 ratio. Enrollment will pause once approximately 150 participants are randomized. Two interim analyses will be performed. The first interim analysis will be performed when approximately 75 participants have completed Week 16 or have terminated study participation. The objective of this interim analysis is to assess whether favorable efficacy is seen in the 1050 mg bermekimab dose group.

The second planned interim analysis will take place once the 150 participants have completed study participation to Week 16 or have terminated study participation. The objectives of the second interim analysis are to assess whether a favorable efficacy is seen in the 1050 mg bermekimab dose group if not determined as favorable at the first interim analysis or confirm the favorable efficacy observed from the first interim analysis, or efficacy is low enough to consider termination of the study or the observed efficacy suggests modification to study.

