If favorable efficacy is observed in either the first or the second interim analysis, screening and randomization of participants will resume in Part 2 as planned, with additional participants being randomized to receive bermekimab 1050 mg qw, placebo, bermekimab 1050 mg qw→q2w, or bermekimab 700 mg qw→q2w in a 1:1:2:2 ratio (approximately 25 participants randomized to receive bermekimab 1050 mg qw and placebo, respectively, and approximately 50 participants randomized to receive bermekimab 1050 mg qw→q2w and bermekimab 700 mg qw→q2w, respectively).

However, if 700 mg qw→q2w is not included in Part 2 based on PK results from Part 1, screening and randomization of participants will resume with additional participants being randomized to receive bermekimab 1050 mg qw, placebo, or bermekimab 1050 mg qw→q2w in a 1:1:2 ratio (approximately 25 participants randomized to receive bermekimab 1050 mg qw and placebo, respectively, and approximately 50 participants randomized to receive bermekimab 1050 mg qw→q2w). Thus, if the study continues, a total number of approximately 250 or 300 participants will be enrolled in the study.

Otherwise, enrollment will remain paused while the sponsor considers whether to terminate the study at that point for insufficient efficacy, to resume enrollment as planned, or to resume the study with modification.

The requestor must use his or her own user identification and personal identification number when contacting the IWRS and will then give the relevant participant details to uniquely identify the participant.

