### **9.2. Sample Size Determination**

This study is designed to enroll approximately 250 or 300 participants, in order to provide sufficient data to have adequate power for the primary endpoint.

The sample size of 250 or 300 participants was also chosen in order to:

- Have sufficient power to detect a difference between the bermekimab groups and the placebo group for the primary endpoint of the proportion of participants achieving HiSCR50 at Week 16 between the bermekimab treatment group and the placebo group in Part 1 and at

Week 12 between bermekimab treatment groups and placebo group combining Part 1 and Part 2.

- Have an adequate confidence level for the treatment difference between the bermekimab high dose group and the adalimumab group in HiSCR50 at Week 16 in Part 1.
- Provide greater precision for the interim analysis efficacy analysis with more participants in the bermekimab 1050 mg, adalimumab, and placebo groups.

The assumptions for the sample size and power calculations specified below were mainly based on the clinical data from the 77474462HDS2002 (PT-047) Phase 2 clinical study and from 2 adalimumab (Humira) Phase 3 clinical studies M11-313 (PIONEER I) and M11-810 (PIONEER II) that evaluated the safety and efficacy of adalimumab in the treatment of adult participants with moderate to severe HS.

The response rates observed in the 77474462HDS2002 (PT-047) study for HiSCR50 at Week 12/Week 16 were 55%/57% (bermekimab qw group), 44%/52% (bermekimab q2w group), and 44%/44% (placebo group), respectively. In addition, the HiSCR50 response rates in the adalimumab Phase 3 Studies M11-313 and M11-810 at Week 12 were 42% vs 26% and 59% vs 28% in the adalimumab weekly and placebo groups, respectively.

Comparisons between treatment groups at Week 16 with Part 1 data (all comparisons are at a 2-sided type 1 error rate of 0.10; [Table 1](#) and [Table 2](#))

- For comparison between bermekimab with placebo using data from Part 1 only for the primary endpoint at Week 16, the study sample size provides 83% power to detect a 25% treatment difference (50% vs 25%) with 50 participants per arm.
- Greater than 99% power to detect a 40% (75% vs 35%) difference between the bermekimab 1050 mg treatment group (n=50) and the placebo group (n=50).

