- From comparison between adalimumab with placebo using data from part 1 only for the primary endpoint, the study sample size provides 83% power to detect a 25% (50% vs 25%) treatment difference with 50 participants per arm.

No formal comparisons will be performed between the bermekimab 1050 mg qw group and the adalimumab group from Part 1, however the treatment difference and its 2-sided 80% CI for the primary endpoint at Week 16 between these 2 groups will be provided. A sample size of 50 participants in each of the treatment groups will produce a 2-sided 80% CI for the treatment difference with a width of approximately 29%.

Comparisons between treatment groups at Week 12 with combining Part 1 and Part 2 data

Assuming HiSCR50 response rates at Week 12 are 25% to 35% for placebo and 50% to 75% for the bermekimab groups, respectively; based on these assumptions, approximately 250 participants across Part 1 and Part 2 are planned to be randomized to the placebo (n=75), bermekimab 700 mg qw to q2w (n=50), bermekimab 1050 mg qw to q2w (n=50), and bermekimab 1050 mg qw (n=75) treatment groups. Comparisons between the bermekimab groups and the placebo groups will be based on data combining Part 1 and Part 2.

For comparisons between bermekimab groups with placebo combining Part 1 and Part 2 for the primary endpoint, bermekimab 1050 mg qw and 1050 mg qw → q2w groups will be grouped together as bermekimab 1050 mg group (n=125) and 700 mg qw → q2w group will be denoted as bermekimab 700 mg group, the study sample size provides:

- At least 87% power to detect a 25% treatment difference between the bermekimab 700 mg treatment group (n=50) and the placebo group (n=75).
- 97% power to detect a 25% (50% vs 25%) treatment difference between the bermekimab 1050 mg treatment group (n=125) and the placebo group (n=75).
- Greater than 99% power to detect a 40% (75% vs 35%) difference between the bermekimab 1050 mg treatment group (n=125) and the placebo group (n=75) or between 700 mg treatment group (n=50) and the placebo group (n=75).

in HiSCR50 at Week 12 combining Part 1 and Part 2 based on a 2-sample Z-test at a Type I error rate of 0.10 (2-sided; [Table 3](#)).

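### Should the pooled Week 12 test of 1050 mg against placebo be stratified by Part as well as by Hurley stage?

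*Protocol*

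**What the plan says.** The first of the three ordered comparisons in Protocol 9.4.2.1.3 is "Bermekimab 1050 mg group versus Placebo at Week 12 based on the combined data from Part 1 and Part 2". For all of them "a CMH chi-squared statistic stratified by baseline Hurley stage status (II, III) at an alpha level of 0.1 will be used". Protocol 9.4.1 names the same single stratification factor for binary endpoints in general, and no section adds Part as a stratum or covariate.

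The allocation is in Protocol 6.3. First, "approximately 150 participants in Part 1 will be randomized to receive bermekimab 1050 mg, adalimumab, or placebo in a 1:1:1 ratio". Part 2 then has "approximately 25 participants randomized to receive bermekimab 1050 mg qw and placebo, respectively, and approximately 50 participants randomized to receive bermekimab 1050 mg" qw→q2w, and these three group sizes are the same whether or not the 700 mg arm is opened. For the Week 12 test the two 1050 mg regimens "will be grouped together as bermekimab 1050 mg group (n=125"), set against 75 placebo participants.

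Planning uses one set of rates for both Parts: "Assuming HiSCR50 response rates at Week 12 are 25% to 35% for placebo and 50% to 75% for the bermekimab groups, respectively" (Protocol 9.2).

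The SAP was written after the study had been stopped. Its Introduction records that the futility criterion was met at the first interim analysis and limits the planned analyses to Part 1. SAP sections 2, 5.3.2.1 and 5.3.3 define and test only HiSCR50 at Week 16 in Part 1. Section 3 still reprints the pooled power tables, but no analysis section carries out the pooled test.

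**The concern.** Randomization protects the comparison within each Part. When two Parts with different ratios are collapsed, Part becomes associated with treatment: 60% of the 1050 mg group but only 33% of the placebo group would come from Part 2. If Part is also associated with response, the pooled comparison is confounded, and stratifying by Hurley stage does not remove that.

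There are reasons to think the Parts could differ. People who have had adalimumab are barred from Part 1 but admitted to Part 2 (Protocol 5.2, criteria 19.1 and 45). Part 2 would also recruit later, without an adalimumab arm and with a higher chance of active treatment.

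The test at issue stands first in the sequence. Upward drift could let the sequence proceed on a false result. Downward drift could close it and make the two later comparisons nominal. Protocol 9.4.2.1.3 claims type I error control at 10% or less, and for the pooled test that depends on a drift near zero, which the protocol neither states nor checks.

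**Working it through.** **Inputs.** Part 1: 50 on 1050 mg, 50 on placebo. Part 2: 25 + 50 = 75 on 1050 mg, 25 on placebo (Protocol 6.3). Two-sided alpha 0.10; 50% vs 25% with 125 vs 75 participants; stated power 97% (Protocol 9.2, Table 3). The drift d (Part 2 minus Part 1 response rate) is an assumption.

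**1. The plan's own power.** Pooled-variance Z-test:
- Mean rate = (125×0.50 + 75×0.25)/200 = 0.40625.
- Null SE = √[0.40625×0.59375×(1/125 + 1/75)] = 0.0717.
- Alternative SE = √[0.25/125 + 0.1875/75] = 0.0671.
- Power = Φ[(0.25 − 1.645×0.0717)/0.0671] = Φ(1.97) = 97.5%.

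This agrees with the stated 97%, which is correct for a common rate in both Parts (d = 0).

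**2. Bias.** With no drug effect and Part rates p1 and p2, the expected pooled rates are:
- 1050 mg: (50p1 + 75p2)/125 = 0.400p1 + 0.600p2.
- Placebo: (50p1 + 25p2)/75 = 0.667p1 + 0.333p2.

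The difference is (0.600 − 0.333)(p2 − p1) = 0.267d. A drift of 5 points gives 1.3 points of bias; 10 points gives 2.7.

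**3. Type I error.** Exact enumeration of all outcomes: CMH without continuity correction, one Hurley stratum, null rate 30% in Part 1, Part 2 always run. The figure in brackets is the error in the drug's favour (nominal 5%).

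| d (points) | Not stratified by Part | Stratified by Part |
|---|---|---|
| −10 | 12.7% (1.8%) | 10.0% (4.9%) |
| −5 | 10.5% (3.1%) | 10.0% (4.9%) |
| −2 | 9.9% (4.1%) | 10.1% (4.9%) |
| 0 | 9.8% (4.9%) | 10.1% (4.9%) |
| +2 | 9.9% (5.7%) | 10.1% (5.0%) |
| +5 | 10.5% (7.2%) | 10.1% (5.0%) |
| +10 | 12.2% (10.2%) | 10.1% (5.0%) |

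A simulation with two Hurley strata (50:50 split and response 10 points lower in stage III, both assumed) gives the same picture for a rise from 25% to 35%: 12.2% with Hurley stage alone, 10.0% with Hurley stage by Part.

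**4. Allowing for the interim decision.** The opening thresholds are not in the documents. As an illustration, suppose Part 2 opens only if Part 1 has more responders on 1050 mg than on placebo, with Week 12 taken as identical to Week 16. That happens in 45.7% of null trials at 30%. Over all trials, two-sided error without Part as a stratum is then 2.0%, 3.1%, 4.8%, 6.9% and 9.5% at d = −10, −5, 0, +5 and +10. At +10 nearly all of the 9.5% favours the drug, against 4.9% when stratified.

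**5. Cost of stratifying.** The Mantel-Haenszel information is 125×75/200 = 46.9 unstratified and 50×50/100 + 75×25/100 = 25 + 18.75 = 43.75 by Part, a ratio of 0.93. Exact power for a 25-point effect at d = 0 goes from 97.5% to 96.6% (placebo 25%) and from 96.6% to 95.8% (placebo 35%). If placebo falls from 35% to 25%, the expected unstratified difference is 25 − 2.7 = 22.3 points, and stratifying raises power from 93.1% to 96.2%.

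**6. What the documents say about d.** Nothing directly. Week 12 placebo rates in the three cited studies are 26%, 28% and 44% (for the earlier bermekimab study, "and 44%/44% (placebo group), respectively"), but that spread is between studies. The only figures by anti-TNF history come from the open-label bermekimab study (Protocol 2.2): 63% of 24 anti-TNF failures and 61% of 18 naive patients at Week 12. Even if every Part 2 participant were anti-TNF experienced, 2 points would give a bias of 0.267×2 = 0.5 points. This evidence is weak. The patients were uncontrolled and all on active drug, and the standard error of that 2-point difference is √(0.63×0.37/24 + 0.61×0.39/18) = 0.15, or 15 points.

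**7. What is actually analysed.** SAP 5.3.3 applies the CMH test to Part 1 alone. One ratio applies throughout, so the mechanism in step 2 cannot operate.

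**The case for a change.** The best argument for changing the plan is that the protection is almost free: one clause, no extra participants and under one point of power. It guards against drift in either direction on the test that controls the whole sequence. Leaving details to the SAP is no full answer, because Protocol 9.4.2.1.3 names its stratum explicitly and the subgroup analyses it promises do not mention Part. Nor does the interim decision cure the problem. It reduces how often the pooled test would be run but leaves the estimate biased, and false superiority could still approach twice its nominal 5%. Protocol 4.1 and 6.3 also let the sponsor resume enrolment as planned after an unfavourable second interim analysis, so the figures with and without an opening rule are illustrations, not properties of the plan.

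All of that stands as design criticism, with two limits. The protocol's error claim is two-sided at 10%. Two-sided error stays close to that for drifts up to about 5 points, and below it under the illustrative opening rule. The doubling in the drug's favour needs a 10-point rise, which nothing in the documents supports or rules out. What does not stand is the step from criticism to amendment, because the test it would repair has been dropped.

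**Conclusion.** The observation is right and the arithmetic holds, but a change would bring no gain. The bias is 0.27d, with d unknown in size and sign. If Part 2 were always run, two-sided error would be 9.8% to 10.5% for drifts within ±5 points and 12.2% to 12.7% at ±10, given a 30% null rate. The protocol's 97% power is correct on its own assumption of common rates. Since the trial stopped after the first interim analysis and the SAP analyses Part 1 at Week 16 only, neither the wording of the pooled test nor any drift between Parts can affect what this study reports. The 700 mg comparison needs no change either. Its use of Part 1 placebo participants is openly stated and is a trade-off of power against reliance on non-concurrent controls. The point is worth remembering if the two-part design is used again: there, stratifying the 1050 mg test and its Mantel-Haenszel difference by Part and Hurley stage would cost 0.8 to 0.9 points of power at d = 0.
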